#### 6.2.6.8 Sleep Diary

A 3-night SHUTi self-reported sleep record diary will be used to provide descriptive information regarding sleep patterns, sleep latency, sleep duration, and sleep disturbances. One diary will be provided at the Entry Visit for all participants in both Study I and Study II and completed for the next 3 days/nights. The study team will call the patient and verbally receive the sleep diary results. For those in Study I, a second diary will be completed for the 3 days/nights after the Week 10 Visit. The study team will again the patient and verbally receive the sleep diary results.

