### 1.2 Study I Secondary Objectives

1.2.1 To compare 10-week changes in Pittsburgh Sleep Quality Index (PSQI) scores and brief sleep diaries between those undergoing insomnia treatment using the SHUTi cognitive behavioral therapy program vs those receiving Usual Care (UC).

1.2.2 To compare 10-week changes in PHQ-9, SF-36, and WHOQOL-HIV Brief scores between those undergoing insomnia treatment using the SHUTi cognitive behavioral therapy program vs those receiving Usual Care (UC).

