### 3.4 Entry Visit for both Study I and Study II

The Entry Visit will occur within 60 days of the routine clinic or phone ISI screening and HIV-1 RNA (viral load) testing that prompted referral to this study. This visit will occur at the Infectious Diseases Research Clinic located at the Fifth Third Office Building on the Eskenazi Hospital campus. After written, informed consent is provided by the participant, a random study code number will be assigned to the participant to ensure confidentiality. This study code number will be used for result reporting and data recording.

At this visit, medical records and current medications will be reviewed. Height, weight, and vital signs will be measured. All participants (both Study I and Study II) will complete the following surveys: ISI, PSQI, Generalized Anxiety Disorder-7 (GAD-7), PANAS (PANAS PA), SF-36, WHOQOL-HIV BREF, and CSRQ-25. All participants will begin the baseline sleep diary entries the night of the Entry Visit, which will be collected verbally over the phone 3 days later. In addition, information on alcohol use, tobacco use, and substance use will be solicited. These questionnaires will be administered in private with availability of the study team to assist only when asked by the participant. The participant may refuse to complete any of the questionnaires.

The participant will then perform the Digit Symbol Substitution Test, the FRAIL Index, and the Fried Index studies.

After these procedures are completed, participants in Study I will be randomized to either the SHUTi intervention or to Usual Care. For participants in Study II, study participation will be considered completed with no further follow-up.

Of note, study participants do not need to be fasting or refrain from smoking for any study visits in this protocol.

Participants who exhibit elevated depressive symptoms ( $\text{PHQ-9} \geq 10$ ) at the final study visit will be urged to follow-up with their primary HIV provider and/or clinical social worker regarding their depression. In addition, the study team will notify the primary HIV provider that his/her patient has completed participation in our trial and still has clinically elevated depressive symptoms. A list of local mental health service providers and clinics will be given to the patients' primary HIV providers or social workers.

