### 3.5 Week 10 Visit for Study I

The participant will come back to the Infectious Diseases Research Clinic for the Week 10 Study Visit. This visit will be scheduled between 63 and 84 days after the Entry Visit. The participant does not need to be fasting nor refrain from smoking at this study visit.

Weight and vital signs will be measured again. Participants will complete again the following surveys: ISI, PSQI, GAD-7, PANAS, SF-36, WHOQOL-HIV BREF, and CSRQ-25. Participants will begin the follow-up sleep diary entries the night of the 10 Week Visit, which will be collected verbally over the phone 3 days later. Questionnaires asking about personal alcohol, tobacco, and substance use will also be administered. These questionnaires will be administered in private with availability of the study team to assist only when asked by the participant. The participant may refuse to complete any of the questionnaires.

The frailty and cognitive function tests performed at the Entry Visit will not be repeated at the Week 10 Visit.

Participants who exhibit elevated depressive symptoms (PHQ-9  $\geq$  10) at this final study visit will be urged to follow-up with their primary HIV provider and/or clinical social worker regarding their depression. In addition, the study team will notify the primary HIV provider that his/her patient has completed participation in our trial and still has clinically elevated depressive symptoms. A list of local mental health service providers and clinics will be given to the patients' primary HIV providers or social workers.

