## 6.0 CLINICAL EVALUATIONS

### 6.1 Schedule of Events

Evaluation	Entry Visit for both Study I and Study II (within 90 days of last clinic-based ISI screening and HIV-1 RNA level assessment)	Weekly SHUTi Sessions for the intervention group in Study I (6 sessions in total)	Week 10 Visit for Study I (for both groups; 63-84 days after Entry Visit)
Informed Consent	X		
Documentation of HIV Status	X		
Medical/Psychiatric History	X		
Medication/Supplement Use History	X		
Diagnoses	X		X
Updated Psychiatric Treatment History			X
Updated Medications			X
Updated Diagnoses			X
Height	X		
Weight	X		X
Vital Signs	X		X
Laboratories obtained through routine clinical care	X		
Questionnaires: ISI, PSQI, PHQ-9, SF-36, WHOQOL-HIV, CSRQ-25, GAD-7, PANAS	X		X
Sleep History and Beliefs Survey (PRE-Treatment)	X		
Sleep History and Beliefs Survey (Post-Treatment)			X
Sleep Diary*	X*		X*
Alcohol, tobacco, substance use questionnaires	X		X
FRAIL Scale (frailty assessment)	X		
Fried Index (frailty assessment)	X		
SPPB Physical Functioning Assessment	X		
DSST Dementia Assessment	X		
Randomization for Study I participants	X		
SHUTi Intervention		X	

\*The study team will call the participant 3 days after the Entry Visit to verbally collect the participants first sleep diary. The study team will again call the participant 3 days after the Week 10 Visit to collect the second sleep diary.

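### The 3-night sleep diaries start on the visit night with no weekday matching, so many participants' two diaries will cover different numbers of weekend nights, adding avoidable random error (not bias) to a secondary outcome

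*Combined protocol and SAP*

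**What the plan says.** Section 1.2 makes the diary a between-arm secondary outcome of Study I: "To compare 10-week changes in Pittsburgh Sleep Quality Index (PSQI) scores and brief sleep diaries between" the SHUTi and Usual Care arms.

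The timing of both diaries is fixed by the visits. At baseline, "All participants will begin the baseline sleep diary entries the night of the Entry Visit" (section 3.4, Entry Visit). At follow-up, "Participants will begin the follow-up sleep diary entries the night of the 10 Week Visit" (section 3.5), and section 6.2.6.8 confirms that "a second diary will be completed for the 3 days/nights after the Week 10 Visit". The footnote to the Schedule of Events (section 6.1) has the results collected by telephone three days after each visit.

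On the Week 10 date, section 3.5 says: "This visit will be scheduled between 63 and 84 days after the Entry Visit". No section sets or matches the weekday, or requires a given number of weekend nights. Section 9.11 promises unadjusted and adjusted comparisons for secondary outcomes but names no covariates.

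Section 6.2.6.8 gives the diary a modest role: "A 3-night SHUTi self-reported sleep record diary will be used to provide descriptive information" on sleep patterns, latency, duration and disturbances.

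**The concern.** A three-night window is short enough for its place in the week to matter. Counting Friday and Saturday as weekend nights, a diary begun on a Monday or Tuesday contains none, one begun on a Wednesday contains one, and one begun on a Thursday or Friday contains two. If a participant enters on a Tuesday and returns on a Friday, any difference between weekday and weekend sleep becomes part of that person's apparent 10-week change.

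The cost is precision. Section 9.2 does not rely on significance; it relies on judging whether effect sizes between the arms are clinically relevant, with about 12 completers per arm. Extra variance widens the interval around a diary effect and shrinks it when standardised. Three nights leave little averaging to absorb the error.

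**Working it through.** **The plan's own figure.** Section 3.1 randomises 16 per arm and section 9.2 expects 25% dropout: 16 × (1 − 0.25) = 12 completers per arm, as stated. The documents give no weekday pattern for visits, no weekend effect on sleep and no SD for the diary, so what follows rests on stated assumptions.

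**Step 1: how often the diaries differ.** Let W be the number of weekend nights in a diary. For visits on Monday to Friday, counting Friday and Saturday nights, W = 0, 0, 1, 2, 2. With visits spread evenly, P(W=0) = 0.4, P(W=1) = 0.2 and P(W=2) = 0.4. If the two weekdays are unrelated:

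- P(same W) = 0.4² + 0.2² + 0.4² = 0.36, so 64% differ.
- P(differ by two nights) = 2 × 0.4 × 0.4 = 32%; the other 32% differ by one.

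If instead the return date is uniform over the Monday-to-Friday dates in the window, 4 of 16 dates repeat the Entry weekday. Among those returning on a different weekday, 0.64 / 0.8 = 80% differ, so overall 0.75 × 0.80 = 60% differ.

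**Step 2: other schedules.** The same enumeration gives the following, where δ is the weekend-weekday difference in the diary measure:

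| Visit days | Nights counted as weekend | Differ, weekdays unrelated | Differ, date uniform in window | SD of added error (unrelated) |
|---|---|---|---|---|
| Mon–Fri | Fri, Sat | 64% | 60% | 0.42 δ |
| Mon–Fri | Sat, Sun | 56% | 52.5% | 0.38 δ |
| All seven days | either pair | 65% | 62% | 0.39 δ |
| Mon–Thu | Fri, Sat | 62.5% | 58% | 0.39 δ |
| Mon, Tue, Fri | either pair | 44% | 40% | 0.44 δ |
| Mon–Thu | Sat, Sun | 37.5% | 35% | 0.20 δ |

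The Monday, Tuesday and Friday row is the case in which the three-day call always falls on a working day. With Monday-to-Friday visits and Friday and Saturday nights, mismatch falls below half once more than 1 − 0.5/0.80 = 37.5% of participants return on the same weekday. With Saturday and Sunday nights the threshold is 1 − 0.5/0.70, about 29%.

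**Step 3: the error added to a change score.** The three-night mean shifts by δ(W₂ − W₁)/3, so the added SD is δ × √E[(W₂ − W₁)²] / 3. In the first row, E[(W₂ − W₁)²] = 0.32 × 1 + 0.32 × 4 = 1.6, and √1.6 / 3 = 0.42.

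**Step 4: size.** Assume an SD of change in sleep duration of 60 minutes with matched diaries, and use the first row:

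| Assumed δ | Added SD | Added variance | 12 per arm is worth | SE of arm difference (24.5 if matched) |
|---|---|---|---|---|
| 15 min | 6.3 min | (6.3/60)² = 1.1% | 12/1.011 = 11.9 | 24.6 min |
| 30 min | 12.6 min | 4.4% | 11.5 | 25.0 min |
| 60 min | 25.3 min | 17.8% | 10.2 | 26.6 min |

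Counting Saturday and Sunday nights gives 0.9%, 3.6% and 14.2%. Varying the assumed SD from 45 to 90 minutes widens the range to 0.4% to 32%. A standardised effect shrinks by the factor 1/√(1 + added variance): under 1%, about 2% and about 8% for the three rows.

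**Step 5: after matching.** Days 63, 70, 77 and 84 are whole weeks after Entry and lie inside the window. On any of them W₂ = W₁ under either definition of the weekend, so this error drops out of the change score. In a baseline-adjusted model with a slope below 1, matching removes less of it; section 9.11 does not say which model applies to the diary.

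**The case against.** The strongest reply is that neither the frequency nor the size can be derived from the documents. Visit weekdays are not given. If follow-up calls are kept to working days, visits fall on Monday, Tuesday or Friday and only 44% of participants are mismatched. If participants tend to come back on the same weekday, the share is lower still. This stands, and it rules out a reading that a reader might infer, that most participants are affected: that follows only from particular scheduling assumptions. It does not remove the error. In the Monday, Tuesday and Friday case every mismatch is by two nights, and the added SD (0.44 δ) is slightly above that of the 64% case.

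The size is also open. At a 15-minute weekend effect the loss is about 1% of variance, and nothing in the documents points to a large effect in this population. If the 60-minute SD already includes unmatched scheduling, the 1% to 18% becomes the share of variance that matching would remove, not an addition to it. The figures cover sleep duration only, not latency or disturbances.

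A reader might also infer that a chance difference in weekday mix between arms is a further harm, or a bias. The documents do not support that. Allocation is randomised and both arms share the same visit window, so such an imbalance is the same random error seen from another side.

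Finally, section 6.2.6.8 calls the diary descriptive, section 9.2 expects no significant differences, and objective 1.2.1 also uses the PSQI. These points keep the matter minor. They do not dispose of it, because section 1.2 still makes diary change a comparison between arms.

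**Conclusion.** The point holds as a minor, avoidable loss of precision in one secondary outcome. The diaries are tied to visit dates, weekdays are not matched, and no covariate for weekend nights is named. Between about 35% and 65% of participants would have different weekend-night counts across the schedules examined; the share exceeds half when visits spread evenly over Monday to Friday and the two weekdays are unrelated. With an assumed weekend effect of 15 to 60 minutes and an assumed 60-minute SD of change, the added variance is about 1% to 18%, which makes 12 completers per arm worth about 11.9 down to 10.2. No bias between arms is expected, and the primary ISI analysis is untouched. The case for acting rests on the low cost of the remedy, not on the size of the harm.

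**What to change.** - **Section 3.5:** add that the Week 10 Visit is booked on the same weekday as the Entry Visit where possible (day 63, 70, 77 or 84), and that the visit is neither delayed nor lost if that weekday does not suit the participant.
- **Section 6.2.6.8:** record the calendar date of each diary night.
- **Section 9.11:** add a sensitivity analysis of the diary outcome that includes the change in the number of Friday and Saturday nights as a covariate for all participants, not only for those whose visits were unmatched.

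No visit, staff or procedure is added. The cost is somewhat less choice of date (four of the 22 calendar days in the window are preferred) and one degree of freedom in the sensitivity analysis, with about 24 completers. The proviso about not losing the visit matters: with 25% dropout expected, securing the Week 10 ISI takes priority over matching the diary.

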#### 6.2.6.9 Fatigue, Resistance, Ambulation, Illnesses, & Loss of Weight (FRAIL) Scale

The FRAIL Scale is a screening test to assess frailty that predicts development of disability, decline in health functioning, and overall mortality (32). Frail scale scores range from 0–5 (i.e., 1 point for each component; 0=best to 5=worst) and represent frail (3–5), pre-frail (1–2), and robust (0) health status. The components and scoring of the FRAIL scale are as follows:

- Fatigue: “How much of the time during the past 4 weeks did you feel tired?” 1 = All of the time, 2 = Most of the time, 3 = Some of the time, 4 = A little of the time, 5 = None of the time. Responses of “1” or “2” are scored as 1 and all others as 0.
- Resistance: “By yourself and not using aids, do you have any difficulty walking up 10 steps without resting?” 1 = Yes, 0 = No.
- Ambulation: By yourself and not using aids, do you have any difficulty walking several hundred yards?” 1 = Yes, 0 = No.
- Illnesses: For 11 illnesses, participants are asked, “Did a doctor ever tell you that you have [illness]?” 1 = Yes, 0 = No. The total illnesses (0–11) are recoded as 0–4 = 0 and 5–11 = 1. The illnesses include hypertension, diabetes, cancer (other than a minor skin cancer), chronic lung disease, heart attack, congestive heart failure, angina, asthma, arthritis, stroke, and kidney disease.
- Loss of weight: “How much do you weigh with your clothes on but without shoes? [current weight]” “One year ago in (MO, YR), how much did you weigh without your shoes and with your clothes on? [weight 1 year ago]” Percent weight change is computed as:  $[(\text{weight 1 year ago} - \text{current weight}) / \text{weight 1 year ago}] * 100$ . Percent change > 5 (representing a 5% loss of weight) is scored as 1 and < 5 as 0.

The FRAIL scale will be assessed only at the Entry Visit.

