## 4.0 SELECTION AND ENROLLMENT CRITERIA FOR BOTH STUDY I AND STUDY II

### 4.1 Inclusion Criteria

- 4.1.1 HIV-1 infection, documented by both: (1) any licensed rapid HIV test or HIV enzyme test kit at any time prior to study entry and (2) by at least one detectable HIV-1 antigen or at least one detectable plasma HIV-1 RNA viral load.
- 4.1.2 Age equal to or greater than 18 years.
- 4.1.3 Ongoing receipt of stable antiretroviral therapy of any kind for at least 3 months prior to the Entry Visit.
- 4.1.4 HIV-1 RNA level  $<$  75 copies/mL obtained during routine clinical care within 90 days of the Entry Visit.

NOTE: There are no CD4 cell count eligibility criteria for this trial.

- 4.1.5 ISI score  $\geq$  11 for Study I and ISI score  $<$  11 for Study II

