### 4.2 Exclusion Criteria

- 4.2.1 Inability to complete written, informed consent.
- 4.2.2 Incarceration at the time of any study visit.
- 4.2.3 Active suicidality, as determined by the patient's HIV provider or social worker following a positive response (1, 2, or 3) to PHQ-9 Item #9 and a positive response (yes) to one or more of the three questions (for Question #3, the previous attempt must be within the past 10 years) on the Patient Suicidality Form (see Appendix).
- 4.2.4 Diagnosed vascular disease (documented history of angina pectoris, coronary disease, peripheral vascular disease, cerebrovascular disease, aortic aneurysm, or otherwise known atherosclerotic disease).
- 4.2.5 History of congestive heart failure, even if currently compensated.
- 4.2.6 Diagnosed disease or process, besides HIV infection, associated with increased systemic inflammation (including, but not limited to, systemic lupus erythematosus, inflammatory bowel diseases, other collagen vascular diseases).

Note: Hepatitis B or C co-infections are NOT exclusionary

- 4.2.7 Known or suspected malignancy requiring systemic treatment within 180 days of the Entry Visit.

NOTE: Localized treatment for skin cancers is not exclusionary.

- 4.2.8 Therapy for serious medical illnesses within 14 days prior to screening.

Note: Therapy for serious medical illnesses that overlaps with a main study visit will result in postponement of that study visit until the course of therapy is completed; postponement outside of the allowed study visit timeframe will result in study discontinuation.

- 4.2.9 Pregnancy or breastfeeding during the course of the study.

- 4.2.10 Receipt of investigational agents, cytotoxic chemotherapy, systemic glucocorticoids (of any dose), or anabolic steroids at the Entry Visit.

Note: Physiologic testosterone replacement therapy or topical steroids is not exclusionary. Inhaled/nasal steroids are not exclusionary as long as the participant is not also receiving HIV protease inhibitors.

- 4.2.11 Active drug use or dependence that, in the opinion of the investigator, would interfere with adherence to study requirements.

- 4.2.12 History of schizophrenia, bipolar disorder, or dementia.

NOTE: Depression is not exclusionary as long as the severity of depression does not impede ability to perform the required study procedures.

- 4.2.13 Musculoskeletal or neurologic disorders that impede ability to perform the required study procedures.

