#### 6.2.5.10 Fried Index

The Fried Index is a measure of frailty (33). It is composed of 5 criteria:

- Self-reported unintentional weight loss of  $\geq 10$  pounds or 5% in the prior year (should be verified with medical records if possible)
- Reduced grip strength (<23 lbs. for women, <32 lbs. for men as measured in the dominant hand using a dynamometer; this is averaged over 3 assessments)
- Self-reported exhaustion (person states they are exhausted 3 or more days per week; exhaustion is feeling “everything I do is an effort” or “sometimes I just cannot get going”)
- Reduced gait speed (>0.8 m/sec over 4 meters; this is averaged over 2 assessments)
- Self-reported low physical activity (being “limited a lot” in vigorous activities from the SF-36 form)

One point is given to each positive criterion with zero points indicating no frailty, 1-2 points indicating pre-frailty, and 3-5 points indicating frailty.

The Fried Index will be assessed only at the Entry Visit.

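### FRAIL and Fried, both Study II primary outcomes, contain items that carry little information as written: an illness point needing in practice 5 of 7 conditions, grip cut-offs in pounds, and a gait inequality that contradicts its label

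*Combined protocol and SAP*

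**What the plan says.** Section 1.3.1 makes FRAIL, the Fried Index and SPPB primary outcomes of Study II, compared between 32 participants with ISI of 11 or more and 12 with a lower score.

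**FRAIL (6.2.6.9).** The illness component is one of five. The first ten entries of its list are given as "The illnesses include hypertension, diabetes, cancer (other than a minor skin cancer), chronic lung disease, heart attack, congestive heart failure, angina, asthma, arthritis, stroke, and"; the eleventh and last entry is disease of the kidney. Its scoring rule is "The total illnesses (0–11) are recoded as 0–4 = 0 and 5–11 = 1".

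**Entry criteria.** Section 4.0 is headed "SELECTION AND ENROLLMENT CRITERIA FOR BOTH STUDY I AND STUDY II". Criterion 4.2.4 excludes "Diagnosed vascular disease (documented history of angina pectoris, coronary disease, peripheral vascular disease, cerebrovascular disease" and further vascular conditions. Criterion 4.2.5 excludes "History of congestive heart failure, even if currently compensated". Cancer is only partly covered: 4.2.7 excludes "Known or suspected malignancy requiring systemic treatment within 180 days of the Entry Visit", so an older cancer can still count.

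**Fried Index (6.2.5.10).** One point is given per positive criterion, for a total of 0 to 5. The grip criterion is "Reduced grip strength (<23 lbs. for women, <32 lbs. for men as measured in the dominant hand using a dynamometer", averaged over three trials. The gait criterion is "Reduced gait speed (>0.8 m/sec over 4 meters; this is averaged over 2 assessments".

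**The concern.** Three scoring lines do not fit the sample or their own labels.

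1. Four of the 11 FRAIL illnesses are barred at entry, yet the cut stays at 5 and the plan does not mention it. The item then separates few participants.
2. The grip cut-offs convert to low values in kilograms for adults aged 18 and over who are well enough to attend the clinic. If the unit is wrong, the item is almost switched off. If it is right, the item is nearly constant.
3. A criterion called reduced gait speed that scores for speeds above a threshold gives the point to the faster walkers.

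At stake is how the Study II frailty comparison can be read. Section 2.3 wants these data to relate insomnia to frailty and to support later trials. If an item is almost constant or scored in the wrong direction, a similar or different composite score in the two ISI groups says less about frailty than it appears to.

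**Working it through.** The plan gives no power calculation for Study II, no illness prevalences and no grip or gait data. The only figure of its own to reproduce is the count of 11 illnesses, and the printed list does contain 11. All prevalences, means and SDs below are assumptions.

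**Step 1. Illnesses left.** Criterion 4.2.4 covers angina, heart attack (as coronary disease) and stroke (as cerebrovascular disease); 4.2.5 covers heart failure. 11 − 4 = 7: hypertension, diabetes, cancer, chronic lung disease, asthma, arthritis and kidney disease. The point still needs 5.

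**Step 2. Chance of the illness point.** With independent illnesses, P(at least 5) is the upper tail of the distribution of the count.

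| Assumed prevalences of the seven, in the order of Step 1 | P(≥5 of 7) | Expected scorers of 44 | P(≥5 of 11), the four added at 5% to 10% each | Expected scorers of 44 |
|---|---|---|---|---|
| Low: .5, .2, .1, .15, .2, .3, .1 | 0.5% | 0.2 | 1.3% to 2.4% | 0.6 to 1.1 |
| High: .6, .3, .2, .3, .3, .5, .2 | 4.3% | 1.9 | 7.1% to 10.4% | 3.1 to 4.6 |

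The exclusions therefore cost about 0.4 to 2.7 scorers among 44.

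With one common prevalence p for all illnesses, the binomial tail with 7 illnesses is 0.02% at p = 0.10, 0.5% at 0.20, 2.9% at 0.30 and 9.6% at 0.40. The last is 44 × 0.096 = 4.2 participants. With 11 illnesses at the same p the figures are 0.28%, 5.0%, 21.0% and 46.7%. That comparison is more severe, because it makes heart attack or stroke as common as hypertension.

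Independence understates the tail. With a latent correlation of 0.1 to 0.3 between illnesses, the low set rises to 1.4%–4.2% and the high set to 7%–13%.

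**Step 3. Grip.** 23 × 0.4536 = 10.4 kg and 32 × 0.4536 = 14.5 kg. The share scoring is Φ((cut − mean)/SD).

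| Group | Assumed mean; SD (kg) | Below cut as printed (lb) | Below cut if the number is kg |
|---|---|---|---|
| Men | 35–45; 8–10 | 0.01% to 2.0% | 5% to 38% |
| Women | 22–30; 5–7 | 0.005% to 4.9% | 8% to 58% |

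Example, men with mean 35 and SD 10: (14.5 − 35)/10 = −2.05 gives 2.0%; (32 − 35)/10 = −0.30 gives 38%.

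**Step 4. Fried total with the gait line as printed.** Assume that grip never scores, that 70% to 95% of participants walk faster than 0.8 m/sec, and that the other three items have prevalences from 5/10/10% to 10/30/30%. The chance that those three are all negative is 0.95 × 0.90 × 0.90 = 0.770 down to 0.90 × 0.70 × 0.70 = 0.441.

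- As printed, P(total = 0) runs from 0.441 × 0.05 = 2% to 0.770 × 0.30 = 23%.
- With the inequality reversed, it runs from 0.441 × 0.70 = 31% to 0.770 × 0.95 = 73%.

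The direction of one sign thus changes the share of participants with no Fried point from a minority to somewhere between a third and three quarters.

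**The case against.** A reader might infer that these lines push the Study II frailty scores to the floor. The documents do not support that. FRAIL keeps four other components, can still reach 4 and so can enter its frail band (3 or more), and its fatigue item may well be common in people with insomnia. SPPB contains neither the illness nor the grip item. The Fried gait line as printed moves totals up.

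Other parts of the opposing case also stand. Most of the rarity of the illness point comes from the cut of 5 itself and would exist without the exclusions. It is too absolute to say that only seven illnesses can occur, because 4.2.4 rests on documented diagnoses whereas FRAIL asks what a doctor ever told the participant. FRAIL is entirely self-reported with or without the illness item, so losing that item does not change its nature. Both ISI groups are scored by the same rules, and section 9.2 does not expect significant differences. The vascular exclusions can also be defended, since cardiovascular disease may confound insomnia and frailty.

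It is also tempting to call the pounds an error. The documents give no grip data and the cited source is not available here, so only a request to verify the unit is supported.

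None of this answers the unresolved unit or the gait line that contradicts its own label.

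**Conclusion.** The point holds as a scoring problem in two of the three Study II primary frailty outcomes.

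- **FRAIL illness item:** weakly informative here. About 0.5% to 4% would score under the assumed independent prevalences, up to about 10% at a prevalence of 0.4 each, and more if comorbidities cluster. The comparison without the exclusions is roughly 1% to 10%, so the loss of sensitivity is modest.
- **Fried grip item:** about 0% to 5% would score as printed and 5% to 58% if the numbers are kilograms, under assumed normal distributions. The unit is undetermined on the documents.
- **Fried gait item:** an internal contradiction that needs no assumption to see. Only its effect on the total, calculated in Step 4, rests on assumed values.

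The grip and gait lines matter most, because each could change the Fried score of a large share of participants. The illness item mainly needs a caveat when FRAIL is interpreted.

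**What to change.** 1. Before any scoring, check the grip unit against reference 33 and the dynamometer display, and correct section 6.2.5.10. In the same edit, reconcile the gait inequality with its label.
2. Record raw grip with its unit for each of the three trials, so that the item can be scored again if needed.
3. Report grip strength, 4-m gait speed and five-repetition chair-stand time as continuous Study II outcomes beside the composites. All three are already measured. State which gait summary is used, since 6.2.5.10 averages two walks and 6.2.5.11 takes the faster.
4. When interpreting FRAIL, state that 4 of its 11 illnesses were excluded at entry.

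The cost is protocol wording, one unit field on the CRF and one extra table, with no new procedures or participants. The drawback is a few more comparisons in 32 versus 12 participants, which should be presented as descriptive. Walking speed and chair-stand time also feed SPPB, so they are not independent evidence.
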